#### 12.6.3 econdary Endpoint Analysis

The following analyses will be carried out on all three analysis populations defined above. ACTitouch® treated subjects will be compared with multi-layer bandaging treated subjects in terms of:

- the difference in changes in HRQOL at 16 weeks assessed by the overall score of the Charing Cross Venous Ulcer Questionnaire using a similar ANCOVA model as used in similar to the Primary Endpoint Analysis. If the primary efficacy analysis was significant, then the difference will be tested at the two-sided  $\alpha=.05$  level.
- the difference in VLU-related outpatient cost per subject at 16 weeks between ACTitouch® treated subjects with multi-layer bandaging treated subjects using non-parametric rank-order, Wilcoxon rank sum tests. If the prior secondary efficacy analysis was significant, then the difference will be tested at the  $\alpha=.05$  level.

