## SYNOPSIS

Title of Study	Randomized Trial Comparing A Dual Action Pneumatic Compression System against Multi-Layer Bandaging Systems: A non-inferiority study
Protocol Date	27 September 2016
Protocol Version	V 2.0
Name of Sponsor	Tactile Medical™
Investigational Product	ACTitouch Adaptive Compression System
Primary Endpoint	Percentage of ulcer area reduction at 16 weeks, comparable
Secondary Endpoint	HRQOL; outpatient cost per subject
Objectives: Demonstrate the following when comparing ACTitouch Adaptive Compression to multi-layer bandaging: 
 
• Comparable rate of healing
 
• Greater improvement in QOL
 
• Lower overall cost of care; lower resource utilization (in clinic time; clinic charges; patient treatment burden)
 
	
METHODOLOGY	
Study Design	Open label, non-inferiority, two arm, prospective, stratified, multi-center, randomized controlled trial (RCT)
Treatments	Daily ACTitouch usage; at least 12 hours sustained mode; two hours of Intermittent Pneumatic Compression (IPC) mode Multi-Layer Bandage (MLB): 24 hours except during clinic visits
Treatment Duration	Run-in – 2 Weeks Study treatment duration – 16 Weeks Follow Up – 3 months (Subjects in the ACTitouch arm who heal during the treatment period.)
SUBJECT POPULATION	
Number Planned	204 randomized subjects; 102 in each study arm

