## 12.0 Data Analysis and Statistical Considerations

### 12.1 Statistical Considerations:

This is a prospective, randomized, stratified, open label, parallel-group, multi-center trial designed to assess the clinical non-inferiority with respect to the percentage of wound area reduction at 16 weeks with the ACTitouch® Adaptive Compression System compared to the Multi-layer Bandaging system in subjects with venous leg ulcer (VLU). Secondary endpoints include health-related quality of life (HRQOL) and Cost of the ACTitouch® Adaptive Compression System compared to the Multi-layer Bandaging system in subjects with VLU. Two hundred and four (204) subjects will be randomized 1:1 into 2 arms, ACTitouch® and Multi-layer Bandaging Systems. Subjects will receive follow-up evaluations at regularly scheduled clinic visits during 16 weeks of follow-up. Subjects will be randomized to 4 strata based on ulcer size and duration (age):

- Size of Ulcer
  - $1.5\text{cm} \leq \text{size} \leq 12\text{cm}$
  - $12\text{cm} < \text{size} \leq 50\text{cm}$
- Age of Ulcer
  - $1 \leq \text{age} \leq 6$  months
  - $6 < \text{age} \leq 24$  months

Subjects will be randomized to treatment groups within strata using a web-based randomization process.

Unless otherwise specified, all safety data, efficacy data, demographic data, and other baseline characteristics will be summarized by treatment group. Continuous data will be summarized by reporting the number of observations, mean, standard deviation, median, minimum and maximum values. Categorical data will be described using frequency tables showing the number and percentage of subjects falling within a particular category.

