Efficacy analysis and associated p-value calculation are described below and will be further elaborated in the Statistical Analysis Plan (SAP) issued prior to database lock. Statistical tests will be performed at a one-sided alpha of .025 for non-inferiority and two-sided alpha level of 0.05 for all other comparisons, unless otherwise specified. Between-group analyses will employ analysis of covariance (ANCOVA) with stratum and treatment group as covariates for continuous data, and chi-square or Cochran-Mantel Haenzel (CMH) methods for stratified categorical data. Kruskal-Wallis tests will be used to compare ordinal variables stratified by ulcer age, wound area and treatment group. If serious departures in the assumptions of normality and homogeneity of variance occur, nonparametric methods will be used for continuous data.

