#### 12.3.2 econdary Endpoints

The secondary endpoints in clinical order of prioritization are as follows:

- the difference in changes in HRQOL at 16 weeks using the overall score of the Charing Cross Venous Ulcer Questionnaire.
- outpatient cost per subject at 16 weeks

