#### 12.6 Analysis Plan:

##### 12.6.1 General Analysis Issues:

Statistical analysis will be performed using SAS Version 9.4 or higher. Non-inferiority analyses will be considered statistically significant at the

one-sided  $\alpha=.025$  level. All other p-values presented will be two-sided and will be considered statistically significant at the two-sided  $\alpha=.05$  level of significance unless otherwise noted. Statistical testing of the primary and secondary endpoints (Stage I) will be performed in hierarchical fashion. The primary efficacy analysis will be performed at the one-sided  $\alpha=.025$  level. If the primary efficacy analysis is statistically significant then the first secondary end point will be analyzed at the two-sided  $\alpha=.05$  level. If this analysis is statistically significant, then the second secondary end point will be analyzed at the two-sided  $\alpha=.05$  level. Otherwise, testing on secondary endpoints will cease and the treatment will not be considered beneficial on either secondary endpoint. P-values for exploratory endpoints will not be adjusted for multiple comparisons.

Baseline demographic and background variables will be summarized by treatment group and strata. For categorical variables, frequencies and percentages will be presented. For continuous variables, descriptive statistics including: sample size, mean, standard deviation, minimum, and maximum, will be presented. Continuous variables will be compared between treatment and control groups using ANCOVA. Categorical variables will be compared between treatment and control groups using the Kruskal-Wallis tests.

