#### 12.6.4 xploratory Endpoint Analysis

- To compare the difference in the incidence of subjects with 100% healed VLUs at 16 weeks between ACTitouch® treated subjects with multi-layer bandaging treated subjects based on logistic regression with the same covariates as used in the Primary Endpoint Analysis.
- To compare the difference in ulcer-free days at 16 weeks between ACTitouch® treated subjects with multi-layer bandaging treated subjects based on non-parametric analysis of covariance using the same covariates.
- To compare the difference in changes in HRQOL at 16 weeks compared to baseline between ACTitouch® treated subjects with multi-layer bandaging treated subjects using the physical component score of the SF-36 using the same method as the Primary Endpoint Analysis.
- To compare the difference in VLU-related outpatient cost per subject for subjects with 100% healed VLU at 16 weeks between ACTitouch® treated subjects with multi-layer bandaging treated subjects using non-parametric rank-order, Wilcoxon rank sum tests.
- To compare the difference in outpatient cost per subject for subjects without 100% healed VLU at 16 weeks between ACTitouch® treated subjects with multi-layer bandaging treated subjects using non-parametric rank-order, Wilcoxon rank sum tests.
- To compare the difference in the time-to-100% healed VLU between ACTitouch® treated subjects with multi-layer bandages treated subjects using a Cox Proportional Hazard model with the same covariates as above.
- To compare the cumulative incidence graphs of subjects with 100% percent healed VLU between ACTitouch® treated subjects with multi-layer bandaging treated subjects using Kaplan-Meier product-moment estimates.
- To compare total VLU-related cost per subject (including cost of scheduled VLU-related study visits, VLU-related inpatient admissions, non-study ACTitouch® treated subjects with multi-layer bandaging treated subjects using non-parametric rank-order, Wilcoxon rank sum tests.

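### The gatekept outpatient-cost test is an unstratified Wilcoxon test: it gives up power by ignoring the randomization strata, and it comes with no interval for the difference in mean cost

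*Protocol*

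**What the plan says.** The Synopsis lists among its objectives "Lower overall cost of care; lower resource utilization". Protocol 12.3.2 makes this the second of two ordered secondary endpoints: "outpatient cost per subject at 16 weeks". No section says whether the quantity to be compared is a mean, a median or something else.

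The endpoint is confirmatory. Protocol 12.6.1 sets a fixed sequence of primary, quality of life, then cost: "If this analysis is statistically significant, then the second secondary end point will be analyzed at the two-sided" 0.05 level. Section 12.6.3 gives the cost alpha without its sidedness, but 12.1 supplies it: "two-sided alpha level of 0.05 for all other comparisons, unless otherwise specified".

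The only analysis named for cost is in 12.6.3: "using non-parametric rank-order, Wilcoxon rank sum tests. If the prior secondary efficacy analysis was significant". That item names no stratification, covariate, effect measure or interval.

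On the strata, 12.1 says: "Subjects will be randomized to treatment groups within strata using a web-based randomization process". There are four, from two levels of ulcer size and two of ulcer duration. The general rule in 12.1 for continuous data is ANCOVA with stratum as a covariate. Its fallback to nonparametric methods does not mention strata.

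The abbreviated SAP contains no cost analysis and no cost table.

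**The concern.** There are two separate issues.

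**Strata.** When allocation is balanced within strata and the strata predict the outcome, the arms differ by chance less than simple randomization would allow. An unstratified rank test still uses the larger, simple-randomization variance. Its statistic is then under-dispersed, so the test is conservative and loses power. Ulcer size and duration plausibly affect outpatient cost, but the documents do not say how strongly.

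**Target of the test.** A rank-sum test asks whether a subject in one arm tends to cost less than a subject in the other. A payer reading a claim about lower overall cost of care will usually think of total cost divided by subjects, the arithmetic mean. Costs are commonly skewed, and if the skewness differs between arms the two quantities can disagree in direction. With no interval for the mean difference, the plan offers no formal way to see that.

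At stake are a real saving missed at the last step of the hierarchy, or a significant result over-read as lower mean cost.

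**Working it through.** **Inputs.** From the documents: 204 subjects randomized 1:1, so 102 per arm; two-sided alpha 0.05; four strata. The documents give no cost SD, expected difference or power for cost, so there is no stated figure to reproduce. All cost distributions and strata effects below are assumptions.

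**1. The passages side by side**

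| Analysis | Status | Uses the stratification factors? |
|---|---|---|
| Percentage area reduction (12.6.2) | primary | yes, ANCOVA with size and duration categories |
| Charing Cross score (12.6.3) | first secondary | yes, similar ANCOVA |
| Outpatient cost (12.6.3) | second secondary, gatekept | none named |
| Ulcer-free days (12.6.4) | exploratory | yes, nonparametric ANCOVA with the same covariates |

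An exploratory endpoint that also gets a rank method is adjusted. The confirmatory cost endpoint is not.

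**2. Effect of omitting the strata.** Let R² be the share of log-cost variance explained by the strata. With balance inside strata, the unstratified z-statistic has variance of about 1 − R² instead of 1. Hence approximately:

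- type I error = 2Φ(−1.96/√(1−R²))
- power = Φ(2.80 − 1.96/√(1−R²)), where 2.80 = 1.96 + 0.84 corresponds to 80% power for the stratified test.

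Example at R² = 0.20: 1.96/√0.80 = 2.19. Type I error is 2Φ(−2.19) = 2.8%, and power is Φ(0.61) = 73%.

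The simulation used 102 per arm, equal strata and 20,000 runs per row:

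| R² | Wilcoxon type I, formula | simulated | Wilcoxon power, formula | simulated | van Elteren power, simulated |
|---|---|---|---|---|---|
| 0 | 5.0% | 4.9% | 80% | 80% | 80% |
| 0.10 | 3.9% | 3.8% | 77% | 77% | 80% |
| 0.20 | 2.8% | 2.9% | 73% | 73% | 80% |
| 0.30 | 1.9% | 1.8% | 68% | 67% | 79% |
| 0.40 | 1.1% | 1.1% | 61% | 59% | 80% |
| 0.50 | 0.6% | 0.6% | 51% | 50% | 79% |

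Van Elteren type I error stayed at 4.8-5.1%. Unequal strata (45/25/20/10%) gave nearly the same results.

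**3. Ranks against means.** For log-normal costs, with log-SD s₁ for the device arm and s₂ for control:

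- median ratio = mean ratio × exp(−(s₁² − s₂²)/2)
- P(device subject costs less) = Φ(−ln(median ratio)/√(s₁² + s₂²)).

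Take device mean 20% higher, s₁ = 1.2 and s₂ = 0.6. The median ratio is 1.2 × exp(−0.54) = 0.70, and P = Φ(0.358/1.342) = Φ(0.267) = 0.61. The rank test therefore favours the device although its mean is higher. Simulated results:

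| Mean ratio | s₁, s₂ | Wilcoxon: device cheaper | Wilcoxon: device dearer |
|---|---|---|---|
| 1.0 | 0.6, 0.6 | 2.6% | 2.4% |
| 1.0 | 0.8, 0.6 | 28% | 0.1% |
| 1.0 | 1.0, 0.6 | 77% | 0% |
| 1.2 | 1.2, 0.6 | 73% | 0% |
| 0.8 | 0.4, 0.9 | 0.2% | 18% |
| 0.8 | 0.6, 0.6 | 73% | 0% |

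With matching shapes (last row) the rank test does well: 73% power against 68% for a Welch test of means. Disagreement needs unequal skewness.

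**4. Sensitivity to a high-cost tail.** Assume medians of $2,400 (device) and $3,000 (control) with log-SD 0.5. The means are 2,400 × e^0.125 = $2,720 and 3,000 × e^0.125 = $3,399. Give 6% of device subjects an extra cost T. The means are equal at T = (3,399 − 2,720)/0.06, about $11,300.

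- T = $20,000, device arm only: Wilcoxon calls the device cheaper in 57% of trials, and in 42% it does so while the observed device mean is higher.
- T = $5,000, device arm only: that conflict falls to 0%.
- T = $20,000, 6% of both arms (device mean 2,720 + 1,200 = $3,920 against $4,599, 15% lower): Wilcoxon is significant in 78% of trials, Welch in 17%.

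**The case against.** The strongest reply is that a rank test is a sensible pre-specified choice for skewed costs. It compares per-subject cost between arms, is valid for the null hypothesis of identical distributions, and can be far more powerful than a test of means (78% against 17% above). No section defines the endpoint as a mean. The endpoint is outpatient cost, and inpatient admissions enter only an exploratory total, so a large one-sided tail is an extreme assumption. Section 12.1 already calls for means and SDs by arm, so a contradicting mean would be visible. All of this stands. It rules out replacing the rank test, and it limits the point about means to reporting an estimate with its interval.

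It may also be said that the test is called unstratified only because 12.6.3 is silent. This does not stand. The rule in 12.1 that stratifies Kruskal-Wallis tests concerns ordinal variables, and the SAP table note on controlling for stratification concerns adverse events. Neither covers cost.

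A reader might also link this point to the exploratory cost comparisons among healed and among unhealed subjects (for example "outpatient cost per subject for subjects with 100% healed VLU at 16 weeks"), or to the different visit schedules of the arms. The former lie outside the testing hierarchy. Whether scheduled-visit costs are itemized cannot be judged, because the economic sub-protocol (Appendix G) is not available. Neither bears on the gatekept test.

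**Conclusion.** The concern holds as an efficiency, consistency and reporting gap. The gatekept cost test does not use the strata that governed randomization, while the neighbouring analyses do. The loss from 80% power is about 2-3 points if the strata explain 10% of log-cost variance, 7 at 20% and 20 at 40%. The true share is unknown, and at zero nothing is lost. The test also supplies no estimate of the mean cost difference and can disagree with it in direction if skewness differs between arms. Whether it will differ cannot be told from the documents.

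Two stronger readings are tempting and are not supported. One is that the test fails to address cost per subject: it does compare per-subject costs, by rank, and the documents never fix the measure as a mean. The other is that omitting the strata inflates false positives: it does the reverse, with type I error falling from 5% to about 3% at 20% of variance explained. The rejections at equal means in step 3 of the check reflect distributions that truly differ, so they are not errors under the null that the rank test addresses.

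**What to change.** In Protocol 12.6.3, and in a cost paragraph and table added to the SAP:

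1. Make the confirmatory cost test a Wilcoxon test stratified by the four randomization strata (van Elteren), two-sided 0.05. Alternatively, use the nonparametric ANCOVA already specified for ulcer-free days. Name one of the two in advance.
2. Beside it, report the difference in arithmetic mean cost per subject with a 95% bootstrap interval resampled within arm and stratum.
3. State that any claim of lower cost is to be read together with that interval, so that a significant rank test is not presented alone as a saving in mean cost.
4. Keep the rank test as the gatekept test, and do not move the confirmatory claim to a comparison of means.

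This needs a few sentences and a little more code, with no new data, no change in sample size and no change to the hierarchy. The drawback is that the interval for the mean difference may be wide if a few subjects are very expensive.

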#### 12.6.4 xploratory Endpoint Analysis

- To compare the difference in the incidence of subjects with 100% healed VLUs at 16 weeks between ACTitouch® treated subjects with multi-layer bandaging treated subjects based on logistic regression with the same covariates as used in the Primary Endpoint Analysis.
- To compare the difference in ulcer-free days at 16 weeks between ACTitouch® treated subjects with multi-layer bandaging treated subjects based on non-parametric analysis of covariance using the same covariates.
- To compare the difference in changes in HRQOL at 16 weeks compared to baseline between ACTitouch® treated subjects with multi-layer bandaging treated subjects using the physical component score of the SF-36 using the same method as the Primary Endpoint Analysis.
- To compare the difference in VLU-related outpatient cost per subject for subjects with 100% healed VLU at 16 weeks between ACTitouch® treated subjects with multi-layer bandaging treated subjects using non-parametric rank-order, Wilcoxon rank sum tests.
- To compare the difference in outpatient cost per subject for subjects without 100% healed VLU at 16 weeks between ACTitouch® treated subjects with multi-layer bandaging treated subjects using non-parametric rank-order, Wilcoxon rank sum tests.
- To compare the difference in the time-to-100% healed VLU between ACTitouch® treated subjects with multi-layer bandages treated subjects using a Cox Proportional Hazard model with the same covariates as above.
- To compare the cumulative incidence graphs of subjects with 100% percent healed VLU between ACTitouch® treated subjects with multi-layer bandaging treated subjects using Kaplan-Meier product-moment estimates.
- To compare total VLU-related cost per subject (including cost of scheduled VLU-related study visits, VLU-related inpatient admissions, non-study ACTitouch® treated subjects with multi-layer bandaging treated subjects using non-parametric rank-order, Wilcoxon rank sum tests.
- Subjects who are assigned to the ACTitouch device and heal during the 16 week treatment period will continue to be seen monthly for each of 3 months ( $\pm 7$  days) post healed visit. At the visit the subject will undergo the procedures outline in the Study Schedule of Activities table in section 7.17. For such subjects, the recurrence rate (percent of subjects who are no longer 100% healed) at months 1, 2 and 3 will be tabulated. Descriptive statistics of the percentage of wound area reduction will be tabulated at each of the 3 monthly

visits. The percentage of non-compliant patients will also be presented at each month.

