### 12.2 Objectives:

The primary efficacy objectives are:

- Assess the non-inferiority of chronic VLU closure at 16 weeks with ACTitouch® therapy compared to a standard regimen of multi-layer bandaging.

The secondary and exploratory efficacy objectives include assessment of the effect of ACTitouch® compared with multi-layer bandaging treated subjects on:

- HRQOL
- outpatient cost per patient
- incidence of 100% healed VLU
- ulcer free days
- outpatient cost per patient healed
- outpatient cost per patient not healed
- time-to-100% healed
- cumulative incidence of 100% healed
- total cost per patient (including inpatient costs)

The safety objective is to compare ACTitouch® treated subjects to multi-layer bandaging treated subjects at 16 weeks in terms of the incidence of ulcer-related adverse events including infections, maceration, allergic reaction to dressing, hospitalization for worsening VLU.

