#### 12.3.3 xploratory Endpoints

- the incidence of subjects with 100% healed VLUs at 16 weeks
- ulcer-free days at 16 weeks
- HRQOL at 16 weeks using the overall and physical scores of the SF-36.
- outpatient cost per subject for subjects with 100% healed VLU at 16 weeks
- outpatient cost per subject for subjects without 100% healed VLU at 16 weeks
- time-to-100% healed VLU
- cumulative incident of 100% healed
- total cost per patient (including inpatient costs)
- ease of use
- treatment satisfaction
- limb volume changes
- compliance

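### Exploratory between-arm cost tests within healed and within not-healed subjects condition on a treatment outcome and can be biased in either direction

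*Protocol*

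**What the plan says.** Protocol 12.3.3 lists two exploratory endpoints split by healing: "outpatient cost per subject for subjects with 100% healed VLU at 16 weeks" and "outpatient cost per subject for subjects without 100% healed VLU at 16 weeks". Protocol 12.6.4 turns each into a between-arm Wilcoxon rank sum test: "To compare the difference in VLU-related outpatient cost per subject for subjects with 100% healed VLU at 16 weeks" and "To compare the difference in outpatient cost per subject for subjects without 100% healed VLU at 16 weeks". Neither test has covariates, an adjustment for selection, or a caveat. Protocol 12.6.1 leaves exploratory p-values unadjusted at the two-sided 0.05 level.

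The variable that defines the subsets is itself an outcome compared between arms in the same section: "To compare the difference in the incidence of subjects with 100% healed VLUs at 16 weeks", by logistic regression. Time to healing is also compared, by a Cox model.

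Two other cost comparisons do not condition on healing. The second secondary endpoint (12.6.3) is "the difference in VLU-related outpatient cost per subject at 16 weeks between ACTitouch® treated subjects with multi-layer bandaging treated subjects", tested hierarchically. Total VLU-related cost per subject is an exploratory comparison in 12.6.4.

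The abbreviated SAP, which presents the tables and figures to be produced, contains no cost analysis and no cost table.

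**The concern.** Randomization makes the two whole arms comparable. It does not make healed ACTitouch subjects comparable with healed control subjects, or the unhealed with the unhealed, because treatment helps decide who falls in each subset.

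Cost is tied to that split. Under Protocol 6.4, treatment visits run for 16 weeks or until healing, so a late healer accrues more visits than an early one, and an unhealed subject the most. If one arm heals additional slow ulcers, its healed subset gains costlier patients, and its not-healed subset can lose its less costly ones. Either subset can then show a cost difference that no patient experiences. If ACTitouch heals fewer ulcers, the distortion runs the other way and flatters it. Equal healing rates are no safeguard if different kinds of ulcer heal on each arm.

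Lower cost of care is a stated objective in the Synopsis, so a small p-value from either test is likely to be read as evidence about cost.

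**Working it through.** **Inputs from the documents.** Sample size: "204 randomized subjects; 102 in each study arm" (Synopsis). Two-sided 0.05, unadjusted (12.6.1). Treatment visits: ACTitouch at weeks 1, 2, 4, 6, 9, 12 and 16, control weekly, both ending at healing (6.4).

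**Not in the documents, so assumed.** Healing rates, unit costs and cost spread. Control healing is set at 40% and ACTitouch at 40% to 60%. The plan states no figure for these comparisons, so there is none to reproduce.

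**Step 1. Equal cost per open week (model A).** One unit per open week in both arms. The 40% who heal on either arm do so uniformly over weeks 4–12 (mean 8). ACTitouch heals a further 10% over weeks 13–15 (mean 14). Unhealed subjects cost 16.

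- Control, all subjects: 0.4×8 + 0.6×16 = 12.8
- ACTitouch, all subjects: 0.4×8 + 0.1×14 + 0.5×16 = 12.6
- Healed subset: (0.4×8 + 0.1×14)/0.5 = 4.6/0.5 = 9.2 v 8.0, so ACTitouch appears 15% dearer
- Not-healed subset: 16 v 16, no distortion

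No patient costs more on ACTitouch and the arm as a whole costs less, yet the healed subset points the other way.

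**Step 2. Graded patient costs (model B).** Easy ulcers (heal on either arm) cost 100, marginal ulcers (heal only on ACTitouch) 160, hard ulcers (heal on neither) 220, SD 30, identical on both arms. With a mix of 40/20/40%:

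- All subjects: 40 + 32 + 88 = 160 in each arm
- Healed: ACTitouch (40 + 32)/0.6 = 120 v control 100
- Not healed: ACTitouch 220 v control (32 + 88)/0.6 = 200

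Here both subsets are distorted by +20. If every ACTitouch patient costs 5 units less, the all-subject result is correctly 155 v 160, but the subsets still show 115 v 100 and 215 v 200.

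**Step 3. How often the planned test misleads.** Simulated trials with 102 per arm: percentage in which the Wilcoxon test finds ACTitouch significantly dearer (nominal 2.5% in that direction).

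| Healing gain (points) | A, healed | B, healed | B, not healed |
|---|---|---|---|
| 0 | 2 | 2.0 | 2.0 |
| 5 | 13 | 11.5 | 9.7 |
| 10 | 38 | 27.4 | 24.2 |
| 15 | 64 | 48.4 | 45.7 |
| 20 | 84 | 66.6 | 67.1 |

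Simulation error moves the model A column by up to about two points. The assumed healing times matter too. At a 10-point gain under A, the figure is 28% if the extra healers spread over weeks 9–15. It is 15% if base healing runs over weeks 2–16 and extra healing over weeks 10–16. Under B with a 20-point gain, the all-subject Wilcoxon test rejects in about 4.8% of trials (2.4% each way), so the conditioning causes the excess.

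**Step 4. Planned visit schedules.** Keep the healing times of model A at a 10-point gain, but count scheduled treatment visits up to the visit at which healing is seen.

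- ACTitouch, base healers: one quarter are seen healed at week 6 (visit 4), three eighths at week 9 (visit 5) and three eighths at week 12 (visit 6), giving 1 + 1.875 + 2.25 = 5.125 visits. Extra healers are seen at week 16 (visit 7).
- ACTitouch, healed: (0.4×5.125 + 0.1×7)/0.5 = 2.75/0.5 = 5.5
- Control, healed: mean of weeks 5 to 12 = 8.5
- All subjects: ACTitouch 2.05 + 0.7 + 3.5 = 6.25; control 0.4×8.5 + 0.6×16 = 13.0

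The healed-subset test then favours ACTitouch in about 100% of simulated trials, and its direction agrees with the all-subject comparison. Conditioning still shifts the contrast: without the extra healers it would be 5.125 − 8.5 = −3.375 visits, and with them it is 5.5 − 8.5 = −3.0. The schedule difference simply outweighs the shift.

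**The case against.** The strongest defence is that nothing confirmatory rests on these tests. Both are exploratory, and the secondary outpatient cost endpoint and the total cost comparison do not condition on healing. That stands, and it limits the consequence to misreading exploratory results. A reader might infer that the trial's cost claim as a whole is compromised; the documents do not support that.

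A reader might also infer that the tests are set to show ACTitouch as dearer when it is not. That needs roughly equal cost per open week, which the documents do not support: they plan 7 ACTitouch visits against weekly control visits, and Step 4 shows that difference dominating. Visit counts do not settle the matter either. They omit device cost, support contacts (6.5) and the monthly post-healing visits that only ACTitouch subjects have (6.6). The trial also expects comparable healing, where the distortion from a difference in rates is smallest.

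A third tempting reading is that the tests fail the objective "outpatient cost per patient healed" in Protocol 12.2, taken as arm total cost divided by number healed. But 12.2 pairs it with cost per patient not healed, and 12.3.3 defines both as costs within the subset. The planned tests match that definition; the ratio is a different estimand that some would prefer.

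Finally, the SAP lists no cost analysis, and Protocol 7.14 refers cost collection to an economic sub-protocol (Appendix G) that is not reproduced. The SAP calls itself abbreviated, so its silence does not withdraw the protocol's endpoints, but their status is unclear.

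**Conclusion.** The point holds for the two subset tests only. They compare groups formed by a treatment outcome that also affects cost, so their p-values are not protected by randomization and can err in either direction. There is no bias when the same patients heal on both arms.

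The size cannot be fixed from the documents. The range from about 2% false findings with no healing gain to 84% at 20 points assumes equal weekly cost in both arms and the stated healing times. Other plausible assumptions give smaller figures, and a difference in visit cost can outweigh the bias. The figures show that the distortion can be material, not that it will be, or which way the net result will point. The secondary and total cost comparisons are unaffected.

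**What to change.** In Protocol 12.6.4:

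- Remove the between-arm Wilcoxon p-values for cost in healed and in not-healed subjects.
- Show cost by healing status within each arm descriptively, noting that the subsets are formed after randomization.
- Base between-arm cost inference on the comparison of all randomized subjects already planned in 12.6.3.
- Use one cost definition for both descriptive summaries. The healed item is limited to VLU-related outpatient cost, while the not-healed item is not.
- State in the SAP whether the cost analyses remain planned and, if so, add their tables.

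Optionally, if cost-effectiveness per healed ulcer is of interest, add each arm's total outpatient cost over all randomized subjects divided by the number healed, with a bootstrap interval resampled within randomization strata. Under model A at a 10-point gain this would be 12.6/0.5 = 25.2 v 12.8/0.4 = 32.0. Its interval may be wider than that of a simple mean.

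The cost is wording and light programming on data already to be collected. The downside is the loss of two exploratory p-values.
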